Study Population: All transgender women undergoing vaginoplasty surgery through the Cleveland Clinic Transgender Surgery & Medicine Program at Cleveland Clinic Main Campus.

Inclusion Criteria:

- Age \geq 18 years of age
- Patients scheduled for full-depth vaginoplasty surgery

Exclusion Criteria:

- Inability to speak or comprehend the English language
- Patients scheduled for no-depth vaginoplasty surgery
- Patients who have undergone previous PFPT

- Patients who are s/p prostatectomy or treatment for prostate cancer

STUDY INTERVENTIONS

Recruitment, Enrollment and Randomization

Patients scheduled to undergo vaginoplasty surgery at Cleveland Clinic Main campus will be approached about voluntary participation in this study. This will occur over the phone approximately one to three months before their scheduled surgery. Patients who agree to participate will be sent a consent form via the mail and will be asked to sign consent in person. Enrollment and randomization will occur following informed consent. All patients will be given a copy of their signed and dated consent.

Once enrolled, patients will be randomized into one of two groups:

- Postoperative PFPT
- No Postoperative PFPT

If patients are randomized into the Postoperative PFPT arm, they will be further randomized into the following sub-arms:

- Postoperative PFPT alone
- Preoperative and Postoperative PFPT

Surgery

All patients will undergo vaginoplasty surgery by a single surgeon in a standard fashion. The neovaginal cavity will be created using the same technique across all patients. Postoperative care will be routine and the same for all patients.

Postoperative Pelvic Floor Physical Therapy

There will be three possible PFPT regimens. All PT regimens will be performed by the same two physical therapists, trained in the management of patients who have undergone vaginoplasty surgery.

- 1) No PFPT

Patients will present to see the physical therapist 3 weeks postoperatively. The following interventions will be performed:

Subjective assessment of bowel and bladder function. Visual and external palpation and assessment of external pelvic floor region. Intravaginal pelvic floor

assessment. Pelvic floor muscle dynamics and coordination assessment. Review of pelvic floor anatomy and function.

2) Postoperative PFPT Only

Patients will present to see the physical therapist 3 weeks and 6 weeks postoperatively. The following interventions will be performed:

3 weeks:

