- Subjective assessment of bowel and bladder function
- Visual and external palpation and assessment of external pelvic floor region
- Intravaginal pelvic floor assessment
- Pelvic floor muscle dynamics and coordination assessment
- Instruction of pelvic floor coordination and lengthening
- Discussion of dilator program and progression
- Home program with instructions

6 weeks:

- External scar assessment and treatment if tissue healing allows
- Instruction to patient of scar mobilizations
- Intravaginal pelvic floor assessment and treatment if indicated
- Review of pelvic floor lengthening and coordination
- Review and progression of dilator program if appropriate
- Assessment of current bowel/bladder symptoms; home program and instructions to address these symptoms

3) Preoperative PFPT and Postoperative PFPT

Patients will present to see the physical therapist 3 weeks before surgery, 3 weeks and 6 weeks postoperatively. The following interventions will be performed:

Preoperative:

- Diaphragmatic breathing
- Discuss dilator positioning/introduce dilator program
- External pelvic floor assessment
- Teach pelvic floor coordination
- Assessment of current bowel/bladder symptoms; home program and instructions to address these symptoms

3 weeks:

- Subjective assessment of bowel and bladder function
- Visual and external palpation and assessment of external pelvic floor region
- Intravaginal pelvic floor assessment
- Pelvic floor muscle dynamics and coordination assessment
- Instruction of pelvic floor coordination and lengthening
- Discussion of dilator program and progression
- Home program with instructions

6 weeks:

- External scar assessment and treatment if tissue healing allows
- Instruction to patient of scar mobilizations
- Intravaginal pelvic floor assessment and treatment if indicated
- Review of pelvic floor lengthening and coordination
- Review and progression of dilator program if appropriate
- Assessment of current bowel/bladder symptoms; home program and instructions to address these symptoms

Study Questionnaires & Exams

All patients will be administered questionnaires preoperatively and 12 weeks postoperatively. The following questionnaires will be administered:

Preoperatively:

- CRAD-8 and UDI-6
- PFIQ-7

Postoperatively 1 week (at the time of routine dilation teaching):

- Vaginal length (routine exam)

Postoperatively 12 weeks:

- CRAD-8 and UDI-6
- PFIQ-7
- PGI-I
- Ease of Passing Dilator (VAS 0-10)
- Pain with Dilation (VAS 0-10)

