- Largest dilator size used
- Vaginal length (routine exam)

Cross-Over Treatment

Any patients in the No PFPT arm who are determined to have pelvic floor dysfunction or symptoms that may benefit from PFPT referral, will be referred after the 12-week mark. Any patient in one of the PFPT arms who is determined to still need PFPT for persistent pelvic floor dysfunction or symptoms will be referred for continued care.

DATA COLLECTION & MANAGEMENT

Data Collection:

In addition to the above-mentioned questionnaires and exam findings, the following data will be collected from the electronic medical record before surgery and 12 weeks postoperatively:

- MRN
- Age
- BMI
- Length of preoperative hormone therapy
- Previous orchiectomy
- Comorbid medical conditions: cardiac, pulmonary, diabetes, autoimmune
- Chronic pain: lower back pain, fibromyalgia, arthritis, other
- Intraoperative complications: bleeding, visceral injury, other
- Postoperative complications: wound issues, hematoma/seroma, infection, anatomic urinary stream issues, fistula, other
- PFPT utilization beyond 6 and 12 weeks postoperatively

Data Management:

Protection of each subject's personal health information will be a priority in this study. One master excel file containing subject personal information including name and medical record number will be kept in a password-protected file, on a designated protected research drive on a password-protected computer in a locked office at the Cleveland Clinic. In that file, each subject will be assigned a subject identification number that will be used for the purposes of data collection in order to de-identify subjects.

All paper forms used for data collection will be kept in a research cabinet dedicated to this project which will be locked at all times, in a locked office at the Cleveland Clinic. All forms will contain de-identified information – identification numbers will correspond to the subjects listed in the master excel file.

[figure not shown]
All study data will be transferred and managed electronically using REDCap (Research Electronic Data Capture). Each subject will be entered into REDCap using the assigned identification number from the master excel file. REDCap is a secure, web-based application designed to support data capture for research studies, providing user-friendly web-based case report forms, real-time data entry validation, audit trials, and a

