JMP 14.0 (SAS Institute Inc., Cary, NC) will be used for all statistical analyses. The primary investigator ([name]) will perform the statistical analysis. All results yielding $p < 0.05$ will be deemed statistically significant.

All analyses will be conducted using an intention-to-treat principle. The investigators anticipate that some non-adherence to the assigned intervention (e.g. crossover to the postoperative PFPT arm) may occur if patients are determined to be symptomatic requiring PFPT per the surgeon's discretion, and as these protocol deviations will bias the results towards superiority of the intervention, a per-protocol sensitivity analysis has also been planned.

REFERENCES

- 4) Jiang DD¹, Gallagher S, Burchill L, Berli J, Dugi D. Implementation of a Pelvic Floor Physical Therapy Program for Transgender Women Undergoing Gender-Affirming Vaginoplasty. *Obstet Gynecol* 2019; 133(5):1003-1011.

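### Crossover of control patients to PFPT would move the intention-to-treat difference towards no difference, not towards superiority as the plan states

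*Combined protocol and SAP*

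**What the plan says.** Four parts of the combined protocol and SAP bear on this.

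- **Analysis principle** (Power Analysis & Statistics): "All analyses will be conducted using an intention-to-treat principle".
- **Expected deviation** (same paragraph): the only example given is "crossover to the postoperative PFPT arm) may occur if patients are determined to be symptomatic requiring PFPT per the surgeon's discretion". No time is attached to it. The paragraph continues: "as these protocol deviations will bias the results towards superiority of the intervention, a per-protocol sensitivity analysis has also been planned".
- **Planned referral** (Cross-Over Treatment): No-PFPT patients who may benefit from PFPT "will be referred after the 12-week mark". For the PFPT arms there is no such time limit; a patient "who is determined to still need PFPT for persistent pelvic floor dysfunction or symptoms will be referred for continued care".
- **Recording** (Data Collection): the item is "PFPT utilization beyond 6 and 12 weeks postoperatively".

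The primary outcome is ease of dilation on a 0-10 visual analogue scale at 12 weeks. It is compared between arms as a difference in means with a t test.

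**The concern.** Under ITT a patient is analysed in the arm to which she was randomized. A control who receives PFPT before the outcome is measured therefore carries any PFPT effect into the control mean. That makes the arms more alike. It cannot create an advantage for PFPT.

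The sentence matters because it is the only reason the plan gives for the per-protocol analysis. A reader who accepts it could take a null ITT result as robust, since the bias supposedly favoured PFPT, when the result may be diluted. The same reader could discount a positive ITT result without cause. A per-protocol estimate lower than the ITT estimate could also be taken as confirming that a pro-PFPT bias had been removed, when selection alone can produce that pattern.

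**Working it through.** **Inputs from the documents.** Difference of 2 points, 80% power, significance level 0.05, 17 evaluable and 20 recruited per arm, outcome at 12 weeks, ITT.

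**Inputs that are assumed.** The crossover fraction before week 12 is not given; 10%, 20% and 30% are used. The SD is not clearly given: the power statement attaches an unlabelled plus-or-minus 1 to the difference. Tests are taken as two-sided.

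**1. The plan's own figure.** With an SD of 1, a t test for a difference of 2 needs 6 per arm. With an SD of 2 it needs 17 (power 80.7%), which matches the plan. SD 2 is therefore used as the illustration. It is one reading, not a stated value. The direction of bias does not depend on it.

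**2. Expected ITT difference.** Let δ be the true effect, c the fraction of controls treated before week 12, and b the average share of the effect they receive (0 to 1).

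- The control mean shifts by b × c × δ.
- ITT difference = δ − b × c × δ = δ × (1 − b × c).

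| True effect δ | b | c = 10% | c = 20% | c = 30% |
|---|---|---|---|---|
| 2 | 1 | 1.8 | 1.6 | 1.4 |
| 2 | 0.5 | 1.9 | 1.8 | 1.7 |
| 0 | any | 0 | 0 | 0 |
| −2 | 1 | −1.8 | −1.6 | −1.4 |

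Every non-zero entry is nearer zero than δ. If no control is treated before week 12, c = 0 and the bias is zero.

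**3. Power, as illustration.** Let r be the correlation between symptoms and a worse untreated dilation score, with the most symptomatic controls crossing over and gaining the full benefit. By simulation with 20 per arm and SD 2, power is 87% without crossover. At 20% crossover (0.20 × 20 = 4 controls) it is 66%, 72% and 78% for r = 0, 0.5 and 1. With SD 1 it stays at about 95% or more even at 30% crossover.

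**4. Per-protocol analysis, if it drops controls who crossed over.** The remaining controls are the less symptomatic ones, so

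per-protocol difference = δ − r × SD × φ(z_c)/(1 − c).

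At c = 20%, φ(z_c)/(1 − c) = 0.350. With SD 2:

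- δ = 2: 2.0 at r = 0; 2 − 0.5 × 2 × 0.350 = 1.65 at r = 0.5; 2 − 1 × 2 × 0.350 = 1.30 at r = 1.
- δ = 0: 0, −0.35 and −0.70, where ITT gives 0 with a 5% rejection rate.

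At these settings with full benefit, per-protocol is further from the truth than ITT once r exceeds 0.4/0.70 = 0.57. Exclusions from the PFPT arm were not modelled and could move the estimate either way.

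**5. As-treated, as a check on other readings.** Moving the crossed-over controls into the PFPT group, at 20% crossover, SD 2 and a true difference of 2, gives 1.42 at r = 0.5 and 0.83 at r = 1. This also falls below 2.

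**The case against.** The strongest case on the other side has four parts.

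- **The example is not exhaustive.** The plan offers crossover only as an example. Extra PFPT in the PFPT arms before week 12 could widen the difference, and continued care there has no time limit. This is a real route in the other direction. But the Cross-Over Treatment section permits that care, so it is not a deviation, and the sentence does not name it.
- **If PFPT made dilation harder,** crossover would flatter it: −2 becomes −1.6. That stands, and it is why the corrected wording should say towards no difference. It is less apparent harm, not superiority.
- **The bias needs a departure from the referral rule.** This stands. If controls are referred only after week 12, the 12-week outcome is untouched.
- **The defect is one clause in a rationale.** ITT is already primary, and the plan gives no rule for reading ITT against per-protocol. This stands too, and it limits the harm to how results could be interpreted.

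Stronger readings are tempting. A reader might infer that the trial is underpowered because of crossover, but the documents give no crossover rate and no clear SD, and with SD 1 the power loss is small. A reader might infer that the two sections flatly contradict each other. The statistics paragraph can instead be read as anticipating departures from the referral rule, so the documents support only that the timing needs reconciling. A reader might also infer that one analysis is known to be nearer the truth. That depends on r and b, which are unknown.

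**Conclusion.** The clause is wrong as written. For the deviation it names, control crossover before the 12-week assessment biases the ITT difference towards no difference. The bias is zero if PFPT has no effect or if no control is treated before week 12. The direction assumes only that PFPT acts in crossed-over controls in the same direction as in the PFPT arm, and no more strongly on average.

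The size cannot be fixed from the documents; the reductions above rest on assumed crossover rates. The point is worth correcting but ranks at the lower end of what should be fixed, because the sample size, endpoint, primary estimate and primary test all stay as they are.

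**What to change.** 1. Replace the clause with: *control crossover to PFPT before the 12-week assessment biases the ITT difference towards no difference.*
2. Keep ITT as the primary analysis.
3. State that the per-protocol analysis is supportive only, because excluding controls selected for being symptomatic can bias against PFPT.
4. Record any PFPT that a control receives before the 12-week assessment. The present item does not clearly cover PFPT before week 6. The text already helps to separate treatment from the scheduled control visit: that visit is assessment plus "Review of pelvic floor anatomy and function", whereas the PFPT visits add items such as "Instruction of pelvic floor coordination and lengthening".
5. Reconcile the Cross-Over Treatment section with the statistics section on when control crossover can occur.

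The cost is one corrected sentence, a caveat on the per-protocol analysis, one small data item and a timing clarification.
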